#### AVG Anastomosis cohort

The effectiveness performance goal of 60% was chosen as it represents the average value reported for stent graft 6-month TLPP for this indication.

For the primary effectiveness endpoint, the treatment ( $P_w$ ) will be compared to the PG by the following hypothesis:

$H_0: P_w \leq 60\%$ ,

$H_1: P_w > 60\%$ ,

Rejection of the null hypothesis will signify that the 6-month TLPP of the WRAPSODY™ Endovascular Stent Graft is greater than the effectiveness PG of 60%.

The safety performance goal of 89% was established by subtracting a 10% margin from the average rate of 99% observed in the literature.

For the primary safety endpoint, the treatment ( $P_w$ ) will be evaluated by the following hypothesis:

$H_0: P_w \leq 89\%$ ,

$H_1: P_w > 89\%$ ,

Rejection of the null hypothesis will signify that the 30-day safety of the WRAPSODY™ Endovascular Stent Graft is greater than the safety PG of 89%.

Sample size for the primary effectiveness endpoint was estimated using the one group exact binomial test. Assumptions included a one-sided 0.05 alpha and at least 90% desired power to show the SG meets the PG. A 74% primary patency rate was assumed in treatment and 60% PG. From these assumptions a sample size of 96 was calculated and with an assumed compliance of 85% yielded 113 subjects.

Sample size for the primary safety endpoint was estimated using the one group exact binomial test. Assumptions included a one-sided 0.05 alpha and at least 99% desired power to show the SG meets the PG. A 98% primary safety rate was assumed in treatment and 89% PG. From these assumptions a sample size of 88 was calculated and with an assumed compliance of 95% yielded 93 subjects.

A final sample size of 113 patients will be used based upon the effectiveness primary endpoint requirements. Study success for this cohort will be declared only if both primary endpoints (safety and effectiveness) meet their performance goals.

## 9.8 Handling of Missing Data

For all primary, secondary and exploratory analyses, no imputation of missing data is planned. In general, endpoint rates will be calculated as the number of subjects who had an endpoint prior to the milestone visit divided by the number of evaluable subjects who had sufficient follow up (e.g., at least 150 days for 6-month visit) plus any subjects who had an event prior to the milestone visit. In other words, the denominator will be adjusted for missing follow up data. A tipping point analysis will be done on the primary endpoints as a missing data sensitivity analysis. This analysis encompasses all possible imputation outcomes and thus is a rigorous set of sensitivity analyses.

## 9.9 Interim Analysis

There is no interim analysis planned with the purpose of altering the Protocol or planned statistical analyses.

## 9.10 Analysis

For the randomized AVF Peripheral cohort, the count and percentage of subjects with TLPP at 6 months will be presented by treatment arm. The percentages will be computed as

$\hat{p}_i = 1 - \frac{n_i}{m_i}, i = T(\text{treatment}), C(\text{control})$ .  $n_i$  is the number of subjects in each treatment arm who experienced non-patency event within 180 days post procedure,  $m_i$  is the number of subjects in each

treatment arm who experienced non-patency event within 180 days or had no non-patency event but followed up for at least 150 days. The hypothesis will be tested using the chi-square test, and the differences between treatments together with a two-sided 95% confidence interval will be calculated. For the primary safety endpoint, the count and percentage of subjects with a safety event at 30 days will be presented by treatment arm. The percentages will be computed as  $\hat{p}_i = 1 - \frac{n_i}{m_i}$ ,  $i = T, C$ .  $n_i$  is the number of subjects in each treatment arm who experienced an event within 30 days post procedure,  $m_i$  is the number of subjects in each treatment arm who experienced an event within 30 days or had no event but followed up for at least 23 days. Non-inferiority on the safety endpoint will be tested using the Farrington-Manning test. The differences between treatments together with the one-sided 95% upper confidence limit will be calculated.

For the nonrandomized AVG Anastomosis cohort, a one-sided p-value will be derived based on an exact binomial test. The study device will be considered to have achieved the primary effectiveness objective if the one-sided p-value is less than 0.05. Or equivalently, the lower limit of the one-sided 95% confidence limit based on exact method is greater than 60%. The same testing methodology will be used for the primary safety endpoint in comparison to the PG of 89%.

To control the overall Type I error (two-sided  $P=0.05$  superiority and one-sided  $P=0.05$  non-inferiority) in the randomized cohorts the following fixed sequence testing procedure will be taken:

Primary effectiveness superiority; if significant at two-sided  $\alpha=0.05$ , proceed to

Primary safety non-inferiority; if significant at one-sided  $\alpha=0.05$  proceed to secondary endpoints.

The key secondary effectiveness endpoint with hypothesis testing is TLPP at 12 months (360 days). Other secondary effectiveness endpoints for hierarchical testing, in order, are:

- ACPP at 6 months (180 days)
- TLPP at 24 months (720 days)
- ACPP at 12 months (360 days)
- ACPP at 24 months (720 days)

Remaining secondary endpoints will be summarized with descriptive statistics, without formal statistical hypothesis testing.

The primary analysis will be completed when all subjects in a cohort complete the 6-month visit (or discontinue prior to the 6-month visit). As this analysis at 6 months (180 days) will be the primary effectiveness analysis and both effectiveness and safety primary endpoints must be met for study success, no alpha adjustment for multiplicity will be applied for this analysis. The final analysis will be completed when all subjects in the intended sample size for each cohort complete the study (24-month visit) and submitted as a post-submission report.

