#### 4.1.2. Primary Effectiveness Endpoint

The primary outcome measure for effectiveness in the WAVE Study is Target Lesion Primary Patency (TLPP) at 6 months. Target Lesion Primary Patency defined as freedom from clinically-driven target lesion revascularization (CD-TLR) or target lesion thrombosis measured through 6 months post-procedure, which is the time interval of uninterrupted patency after study procedure to the next intervention performed on the target lesion or uncorrectable target lesion occlusion.

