#### 5.4 Subject Withdrawal

Subjects may withdraw at any time from the clinical trial without jeopardy or prejudice. If a subject prematurely terminates from the study, the reason for study termination will be recorded and the results will be tabulated by number and percent for each category. If termination is a result of an adverse event or death, an Adverse Event Form will also be completed. Subjects who withdraw consent after treatment will have their data evaluated until the time of their withdrawal.

The Investigator should follow all unresolved SAEs until the events are resolved, the subject is lost to follow-up, the subject has withdrawn consent, the subject completes the study, or the adverse event is otherwise explained.

All reasonable efforts will be made to obtain complete data for all subjects; however, missing observations will occur due to lost to follow-up, withdrawal, or non-adherence with required assessments. Three (3) attempts shall be made to contact subjects who do not return for study follow-up visits. The final attempt shall include a certified letter to the subject regarding study participation. If these subjects cannot be located, they will be considered lost to follow-up. If they are contacted but refuse to return for visits, they

will be considered withdrawals. If they actively request to withdraw from the study, they will be considered withdrawals. Subjects shall be encouraged to complete a final study exit visit at the time of withdrawal to assess for safety. Data collected up to the time of loss to follow-up or withdrawal will be maintained in the study database and used for analysis purposes, as appropriate. These subjects will not be replaced.

Subjects should be withdrawn from the study by the Investigator if any of the following occur as these additional treatments prevent further analysis of patency related endpoints:

- Subject proceeds to renal transplant
- Device is explanted
- Access is abandoned

Investigator may also withdraw subjects from the study for reasons other than above, where they judge this is in the subject's best interest. Data collected up to the time subject is withdrawn from the study will be maintained in the study database and used for analysis purposes, as appropriate. These subjects will not be replaced.

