#### 9.3.2. Primary Effectiveness Endpoint

The primary effectiveness endpoint is the proportion of subjects with target lesion primary patency (TLPP) at 6 months (180 days). The key secondary effectiveness endpoint is the proportion of subjects with TLPP at 12 months (360 days). Calculation of these endpoints will be based on the number of subjects with adequate follow-up. In addition, these endpoints will be estimated using Kaplan Meier estimates with standard error calculated using the Greenwood method. Time to loss of TLPP is defined as the interval of uninterrupted patency from initial study procedure to the next intervention performed on the target lesion.

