**Arteriovenous (AV) Access Abandonment:** When a vascular access can no longer be used for prescribed 1 or 2 needle dialysis because it is unable to provide adequate flows and/or is deemed unsafe for the patient, and the associated problem cannot be corrected by any intervention, including medical, surgical, or radiologic interventions or rest (KDOQI).

**Assisted Target Lesion Primary Patency (aTLPP):** Defined as time to loss of Assisted Primary Patency of the target lesion, which is the time from post-procedure until uncorrectable target lesion occlusion.

**Bleeding Complication (Major):** Bleeding resulting in  $\geq 3$  g/dl decrease in hemoglobin (if hemoglobin level not available, a decrease in hematocrit of  $\geq 10\%$ ), or necessitating transfusion of  $>1$  unit of PRBC's / whole blood or necessitates surgery/endoscopic intervention.

**Access site:** Bleeding from the arteriotomy site which requires transfusion, hospitalization (either admission or extended stay), or further treatment for management.

**Cardiac Arrhythmia:** Electrical disruption of the heart rhythm requiring specific medication, DC shock, or pacemaker insertion to address condition.

**Cardiogenic Shock:** Subject presents with SBP  $< 80$  mm Hg for more than 30 minutes unresponsive to fluids or requiring intravenous vasopressor agent or an intra-aortic balloon pump (IABP).

**Catheter Dysfunction:** The first occurrence of either (1) peak blood flow of 200 ml per minute or less for 30 minutes during a dialysis treatment, (2) mean blood flow of 250 ml per minute or less during two consecutive dialysis treatments, or (3) inability to initiate dialysis owing to inadequate blood flow, after attempts to restore patency have been attempted.

**Cerebral Vascular Accident (CVA):** See Stroke.

**Closure, Abrupt:** Occurrence of new (during the index procedure), persistent slow, reduced, or loss of flow within the target vessel that requires intervention other than the index or adjunct treatment. Abrupt closure may also be referred to as acute occlusion if there is a total loss of flow.

**Closure, Late:** Target lesion site occlusion that occurs greater than 30 days after the index procedure is completed (e.g., the subject has left the treatment area).

**Closure, Subacute:** Target lesion site occlusion that occurs after the index procedure is completed (e.g., the subject has left the treatment area) and within 30 days of procedure.

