**Stent Strut Fracture Types:**

**Type 0:** No strut fractures.

**Type I:** Single strut fracture only.

**Type II:** Multiple single strut fractures that can occur at different sites.

**Type III:** Multiple strut fractures resulting in complete transection of the stent, without displacement of the stent segments.

**Type IV:** Multiple strut fractures resulting in displacement of segments of the stent.

**Stroke:** Any neurological deficit lasting 24 hours or longer, or lasting less than 24 hours with a brain imaging study showing infarction consistent with deficit. May be further categorized as:

- Ischemic Stroke: neurologic deficit meeting the study definition for Stroke that is attributed to thromboembolic event.
- Hemorrhagic Stroke: neurologic deficit meeting the study definition for Stroke that is attributed to bleeding into brain tissue, epidural, subdural, or subarachnoid space; or a combination of these sites.

**Successful Dialysis:** A successful dialysis session includes:

- Normal cannulation *and*
- Is not stopped prematurely

**Target Lesion Primary Patency (TLPP):** Defined as freedom from clinically-driven target lesion revascularization (CD-TLR) or access circuit thrombosis measured through 6 months post-procedure, which is the time interval of uninterrupted patency after study procedure to the next intervention performed on the target lesion or uncorrectable target lesion occlusion

**Target Lesion Revascularization, Clinically-Driven (CD-TLR):** Any re-intervention involving the target lesion in which the subject has clinical or physiologic abnormalities that indicate dialysis access dysfunction.

**Target Lesion Revascularization, Non-Clinically-Driven:** Any reintervention that does not meet the criteria for CD-TLR.

**Thrombocytopenia:** A persistent decrease in the number of blood platelets to subnormal levels.

**Thrombus:** Blood clot that obstructs a blood vessel.

**Transient Ischemic Attack:** A neurological event where symptoms last for less than 24 hours, with no evident permanent functional impairment.

**Vessel Occlusion / Thrombosis at Groin/Access Puncture Site:** Angiographic or ultrasonographic evidence of occlusion at the puncture site limiting antegrade flow to the distal limb.

**Vessel Perforation / Rupture / Puncture of a Vessel Wall:** Classified as follows:

**Angiographic perforation:** Perforation detected by the clinical site at any point during the procedure.

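### Explant and access abandonment trigger withdrawal but are not named as TLPP failures, so a case with no other TLPP event is dropped before Day 150 and scored patent from Day 150 to 180

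*Combined protocol and SAP*

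**What the plan says.** Section 4.1.2 defines TLPP as "freedom from clinically-driven target lesion revascularization (CD-TLR) or target lesion thrombosis measured through 6 months post-procedure", with patency running "to the next intervention performed on the target lesion or uncorrectable target lesion occlusion". Section 9.3.2 is narrower: time to loss is "the interval of uninterrupted patency from initial study procedure to the next intervention performed on the target lesion". Section 13.0 is wider on thrombosis: "freedom from clinically-driven target lesion revascularization (CD-TLR) or access circuit thrombosis measured through 6 months post-procedure". It defines clinically-driven revascularization (CD-TLR) as "Any re-intervention involving the target lesion in which the subject has clinical or physiologic abnormalities that indicate dialysis access dysfunction". None of these names explant or abandonment. By contrast, Section 4.2 names abandonment as a failure of access circuit primary patency (ACPP) and as the end of secondary patency.

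Section 5.4 has the investigator withdraw subjects at renal transplant, explant or abandonment because "these additional treatments prevent further analysis of patency related endpoints". Section 13.0 describes abandonment as loss of a usable or safe access where "the associated problem cannot be corrected by any intervention".

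For the AVF cohort, Section 9.10 computes the 6-month rate as 1 − n/m. Here n counts non-patency events within 180 days, and m adds those who "had no non-patency event but followed up for at least 150 days". Section 9.8 gives the 150-day rule for endpoint rates in general, so it covers the AVG cohort. It rules out imputation and plans a tipping-point analysis of the primary endpoints. Section 9.2 censors a subject without an event at the time of becoming un-evaluable.

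**The concern.** Section 5.4 puts explant and abandonment beside renal transplant, as if patency could no longer be observed. Abandonment is an observed outcome, though: the access has stopped working or is unsafe and cannot be repaired. An explant means that the device under test is gone. If neither is a non-patency event, a poor outcome is handled as missing data or as a success, depending only on its date.

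The AVG cohort is judged against a fixed 60%, so any uncounted failure helps it to pass. In the AVF cohort only the stent-graft arm can have an explant of the study device. A graft removed for infection on Day 60 with flow preserved could fall outside both primary endpoints: the safety window closes at 30 days, and the effectiveness definition does not clearly include it.

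**Working it through.** **1. The plan's own sizes.** AVF: 78% against 60%, two-sided 0.05, 80% power, chi-square with pooled null variance. The formula gives 102.4, so 103 per arm, and 103/0.85 = 121.2, so 122. AVG: with 96 evaluable, the exact one-sided 0.05 test against 60% passes at 66 or more. P(X ≥ 66 | 96, 0.60) = 0.048, and power at 74% is 0.8995. Then 96/0.85 = 112.9, so 113. Both stated sizes reproduce.

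**2. Which cases are uncaptured.**

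| Event by Day 180 | Under the current text |
|---|---|
| Abandonment with target lesion thrombosis, CD-TLR or uncorrectable target lesion occlusion | Failure (4.1.2) |
| Abandonment with thrombosis elsewhere in the circuit | Failure under 13.0, not under 4.1.2 |
| Abandonment for inadequate flow or unsafe access, without occlusion or reintervention | Not named |
| Explant with access dysfunction | Arguably CD-TLR or a target lesion intervention |
| Explant for infection, flow preserved | Not CD-TLR; a failure only if read as an intervention on the target lesion |

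Without a qualifying event, a withdrawal before Day 150 is in neither n nor m. From Day 150 to 180 it is in m but not in n, so it scores as patent.

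**3. AVG pass probability.** Assumptions: a share r of subjects is uncaptured, spread evenly over 180 days (5/6 before Day 150, 1/6 after); the true share of patent subjects, with these cases as failures, is 60%; 96 remain evaluable. The analysed rate is then p = (0.60 + r/6)/(1 − 5r/6).

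| r | p | P(X ≥ 66 given 96, p) |
|---|---|---|
| 0 | 0.600 | 4.8% |
| 0.5% | 0.603 | 5.5% |
| 1% | 0.607 | 6.3% |
| 2% | 0.614 | 8.2% |
| 3% | 0.621 | 10.5% |
| 5% | 0.635 | 16.7% |

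A variant drops every case, p = 0.60/(1 − r), and shrinks the denominator. It gives 6.9% at r = 2% (94 evaluable, cut-off 65) and 13.7% at r = 5% (91 evaluable, cut-off 63).

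**4. Individual results, AVG.**
- At the boundary, 66/96 passes (p = 0.048). One case before Day 150 restored as a failure gives 66/97 (p = 0.064). One case from Day 150 to 180 gives 65/96 (p = 0.074).
- At the design rate, 71/96 has p = 0.003. Two cases restored before Day 150 give 71/98 (p = 0.007). Five before and two after give 69/101 (p = 0.053, goal missed).

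**5. Individual results, AVF (chi-square, no correction).**
- At the boundary, 76/103 against 62/103 has p = 0.038. Two restored failures in the stent-graft arm only (76/105) give p = 0.063. Two in each arm (76/105 against 62/105) give p = 0.042.
- Near the design rates, 80/105 against 62/103, again with two restored in the stent-graft arm only, has p = 0.013.

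**The case against.** The strongest reply is that much of this is already covered. Abandonment following target lesion thrombosis, CD-TLR or uncorrectable occlusion is a failure, and Section 5.4 keeps data up to withdrawal, so an earlier event is not erased. Sections 4.1.2 and 9.3.2 also end patency at the next intervention on the target lesion, and surgical removal of a graft lying in that lesion can be read that way. The Clinical Events Committee (CEC) reviews all endpoints and circuit interventions (12.10). This stands, and it limits the point to the uncaptured cases. It does not close the gap: the protocol gives the committee no rule for these two events, and Section 5.4 points towards unobservable patency.

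The tipping-point analysis can reach the exclusions before Day 150, five-sixths of the cases under even spread. It cannot reach those from Day 150 to 180, which are recorded as observed patent, and it is not the primary test.

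TLPP is also a lesion-level endpoint, and circuit loss is measured by ACPP and secondary patency. That is a fair reason to exempt abandonment unrelated to the lesion. It is not a reason to score such a subject as patent.

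A reader might infer that explant and abandonment are never TLPP failures, that the reported rate is therefore overstated, or that the AVF comparison is biased towards the device. The documents support none of these in full. Some cases count already, the number of others is unknown, and abandonment can follow angioplasty too. An excess of abandonment in that arm would push the AVF difference the other way.

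**Conclusion.** The point holds for explants and abandonments with no qualifying TLPP event. For those, the stated rules can only raise an arm's TLPP, by dropping the subject or by counting a success, and in the AVG cohort this always works towards meeting the goal. Its size cannot be fixed from the documents. At an assumed 0.5% to 5% uncaptured, the one-sided error in the AVG cohort goes from 4.8% to between 5.5% and 16.7%; the upper end needs most such events to escape every existing clause. Single cases change the conclusion only near the boundary; at the design rates a few do not. In the AVF cohort the direction is known for explants (towards the stent graft) and unknown for abandonment. The matter should be settled before the primary analysis, because otherwise the classification rests on an interpretation made after the data exist.

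**What to change.** Reconcile Sections 4.1.2, 5.4, 9.3.2, 9.8, 9.10 and 13.0, and define non-patency event, including which thrombosis counts. For the primary analysis:

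- count explant of the study device as loss of TLPP on the date it occurs;
- count abandonment as loss of TLPP on its date, unless the CEC attributes it to a cause unrelated to the target lesion;
- do not score a subject withdrawn for either reason on Day 150 to 180 as patent;
- add a sensitivity analysis, in both cohorts and both AVF arms, counting every explant and abandonment by Day 180 as failure.

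This changes the analysis only; the clinical withdrawal rules are untouched. Reasons for termination are already recorded under Section 5.4. The costs are a slightly less favourable TLPP, a line in the committee's charter, and a protocol and SAP amendment, which under Section 12.3 may need FDA and then IRB/EC approval. The report should also note that the sources behind the 60% goal may define TLPP differently, which the documents do not show.

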### **1.9 Treatment of Thoracic Central Vein Obstruction**

[figure not shown]
Treatment for symptomatic TCVO is PTA, but neointimal hyperplasia can progress due to damage to the vessel lumen from PTA, and stenosis has been shown to progress faster after intervention. The mechanism of angioplasty involves cracking and disrupting the vessel intima, which can accelerate intimal hyperplasia. Recurrent lesions after PTA have been demonstrated to have a higher proliferative index than the primary lesion.

[figure not shown]
Central veins are more elastic, and therefore, more likely to recoil after PTA than the peripheral veins, with more than 50% of central lesions showing immediate recoil. KDOQI guidelines suggest stent/stent graft placement as a treatment option for acute elastic recoil after PTA, when a stenosis recurs within three (3) months, in subjects at increased risk for surgery, or following vessel rupture.

[figure not shown]
No stent graft has been approved for treatment of thoracic central vein obstruction; consequently, there are no pivotal studies and published data on their effectiveness for this use is limited. In a cohort study by Jones and colleagues, VIABAHN stent grafts were placed in the central veins of 42 subjects with stenosis that did not respond to PTA. Primary patency rate at six (6) months was 81% and 67% at 12 months. As further support, in the RESCUE study summarized earlier, a subset of 96 subjects (total study  $n = 275$ ) with instent stenoses in the central veins demonstrated statistically significantly better TLPP and ACPP at six (6) months for the stent graft group compared to the PTA cohort (TLPP 63.4% vs 4.3%,  $p < .001$ ; ACPP 17.5% vs 2.0,  $p.02$ ). The performance of PTA is exceptionally low in these subjects, perhaps because the balloons could not be inflated sufficiently within the existing stents. It is not likely to be representative of PTA performance in native central veins; however, together, the two (2) studies above suggest that stent grafts placed for the treatment of central venous stenosis are an effective way to maintain luminal patency.

[figure not shown]

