## 6.2 Baseline

[figure not shown]
The following examinations and tests will be performed. For those study procedures that are not considered standard of care (performed only for study participation), they will be performed after the subject signs the informed consent form in order to meet **all** inclusion and **no** exclusion criteria. These examinations and tests will be used both to screen eligible subjects and provide baseline information for those subjects that meet study eligibility criteria.

*All tests must be completed within the 30 days prior to undergoing the index / study procedure, except for the pregnancy test, which must be completed within 14 days of the procedure (if applicable).*

- Demographic information and medical history including, but not limited to, risk factors and hemodialysis and dialysis access history:
  - Type, location and date of all previous venous outflow circuit intervention(s)
  - Prior dialysis access type(s) and location(s)
    - Location of current dialysis access, including date AVF or AVG was first used for dialysis
- Targeted physical examination, including but not limited to:
  - Height and weight
  - Vascular access circuit / fistula assessment including, but not limited to:
    - Presence / absence of steal syndrome
    - Presence / absence of thrill
    - Presence / absence of bruit
    - Presence / absence of infection
- Laboratory Assessments:
  - Urine or serum pregnancy test if female of child-bearing potential (within **14** days of procedure). NOTE: Please review your institutions standard for women of childbearing potential.

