### **6.4.3. Randomization**

Randomization will be used to reduce potential bias during data collection and evaluation of clinical endpoints in the AVF Peripheral cohort. Randomization schedules will be generated using block randomization that will control the balance of treatment groups within each site and across the study. It is not possible for treating physicians to be blinded to the treatment group. Subjects who receive a Merit WRAPSODY Stent Graft must receive a device information card to provide to health care givers in the event they undergo an MRI, so subjects cannot be blinded.

AVF Peripheral subjects will be randomized 1:1 to receive either the Merit WRAPSODY Stent Graft (SG) or PTA. AVG Anastomosis subjects will not be randomized. Once baseline angiography confirms eligibility, including confirmation of reference vessel diameter (RVD), lesion length, full expansion of the predilatation balloon, the patient is eligible to be randomized or enrolled in the AVF Anastomosis cohort.

Subjects randomized to the PTA arm (control) will undergo standard percutaneous balloon angioplasty. Subjects randomized to receive treatment with the Merit WRAPSODY Stent Graft after predilatation will undergo stent graft placement as outlined in Section 6.4.4. Only the target lesion will be treated with the WRAPSODY stent graft.

Note: Subjects in the AVG Anastomosis cohort will all receive treatment with the Merit WRAPSODY Stent Graft as this cohort is non-randomized.

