#### AVF Peripheral cohort

For the primary effectiveness endpoint, the SG treatment ( $p_T$ ) and PTA control ( $p_C$ ) groups will be compared in a superiority format under the following hypothesis.

$$H_0: p_T = p_C$$

$$H_A: p_T > p_C$$

For the primary safety endpoint, the treatment ( $\pi_T$ ) and control ( $\pi_C$ ) groups will be compared in a non-inferiority format under the following hypothesis.

$$H_0: \pi_T \geq \pi_C + 0.15$$

$$H_A: \pi_T < \pi_C + 0.15$$

Sample size for the primary effectiveness endpoint was estimated using the two-group chi-square test. Assumptions included a two-sided 0.05 alpha and at least 80% desired power to show superiority of SG to PTA. A 78% primary patency rate was assumed in treatment and 60% in control. From these assumptions a sample size of 103 per arm was calculated and with an assumed compliance of 85% yielded 122 per arm or 244 in total.

For the one-sided 0.05 test of non-inferiority of SG to PTA on the primary safety endpoint, the event-free safety composite rate was assumed to be 95% in the treatment and control groups with a non-inferiority margin of 15% using the Ferrington-Manning test. Power for non-inferiority of the primary safety endpoint was 80% and the calculated sample size was 40 per arm. After assuming 5% lost to follow-up at 30 days the number per arm was 43 or 86 in total. Therefore, the overall sample size for this study cohort was determined by the effectiveness endpoint. With a total sample size of 244 the safety endpoint will have 99% power.

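### The AVF primary test is a valid unadjusted chi-square that uses no baseline covariates; adjustment could add about 2 to 4 points of power if they explain 5–10% of outcome variance

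*Combined protocol and SAP*

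**What the plan says.** In section 9.10 the AVF primary effectiveness analysis counts subjects who lost patency by day 180 and those with 150 or more days of event-free follow-up. On the comparison itself it states: "The hypothesis will be tested using the chi-square test, and the differences between treatments together with a two-sided 95% confidence interval will be calculated". No covariate enters the test or the interval.

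The sample size in section 9.7 rests on the same test: "Sample size for the primary effectiveness endpoint was estimated using the two-group chi-square test". Its inputs are "Assumptions included a two-sided 0.05 alpha and at least 80% desired power to show superiority of SG to PTA" and "A 78% primary patency rate was assumed in treatment and 60% in control". The result: "From these assumptions a sample size of 103 per arm was calculated", raised to 122 per arm for 85% compliance.

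Several candidate covariates are known before allocation. Section 6.4.3 places randomisation after angiographic eligibility is confirmed, "including confirmation of reference vessel diameter (RVD), lesion length, full expansion of the predilatation balloon". Section 6.2 collects the kind, site and date of earlier outflow interventions, the location of the current access and the date it was first used. Section 4.4.2 admits RVD from 5.0 to 14.0 mm, and section 3.1.3 includes the cephalic arch, so the lesions are mixed. Randomisation is blocked to balance arms within site (6.4.3); the visible text mentions no stratification by lesion type.

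The only regression models in the visible text are the poolability models in section 9.6.

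**The concern.** In a randomised comparison, baseline variables that predict the outcome can be used to shrink the standard error of the treatment difference without changing what is estimated. They also remove the part of a chance imbalance that those variables explain. The plan collects such candidates and leaves them out.

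The stakes come from the position of this test. It is sized at the minimum stated power. Under the fixed sequence in 9.10, safety non-inferiority and then the secondary hierarchy are tested only if it succeeds. Section 9.3 requires both primary endpoints for the cohort to succeed. A few points of power on this endpoint therefore carry through to everything after it.

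**Working it through.** **Inputs from 9.7.** pT = 0.78, pC = 0.60, difference 0.18, two-sided alpha 0.05 (z = 1.960), power 80% (z = 0.842), 1:1 allocation.

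**Step 1: reproduce the plan's figure.** Two-group chi-square, pooled variance under the null, no continuity correction, with mean proportion 0.69:

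n = [1.960·√(2·0.69·0.31) + 0.842·√(0.78·0.22 + 0.60·0.40)]² / 0.18²
= [1.960·0.6541 + 0.842·0.6416]² / 0.0324
= (1.282 + 0.540)² / 0.0324 = 102.4, so 103 per arm.

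103/0.85 = 121.2, so 122 per arm. Both stated figures reproduce. Power at 103 is Φ[(0.18·√103 − 1.282)/0.6416] = Φ(0.849) = 80.2%.

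**Step 2: effect of adjustment.** Let R² be the share of within-arm outcome variance explained by the covariates. The adjusted standard error is about √(1 − R²) times the unadjusted one, so the effective sample size is n/(1 − R²). The documents give no R²; the values below are assumptions.

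| R² (assumed) | Effective n per arm | Power | Gain (points) |
|---|---|---|---|
| 0 | 103 | 80.2% | 0 |
| 0.02 | 105.1 | 81.0% | 0.8 |
| 0.05 | 108.4 | 82.2% | 2.0 |
| 0.10 | 114.4 | 84.2% | 4.0 |
| 0.15 | 121.2 | 86.2% | 6.0 |
| 0.20 | 128.8 | 88.2% | 8.0 |

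At R² = 0.10 the standard error is about 5% smaller (√0.90 = 0.949), equivalent to 11% more subjects (1/0.90 = 1.11). If all 122 per arm were evaluable, power would be 86.5% unadjusted, 88.1% at R² = 0.05 and 89.8% at R² = 0.10.

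**Step 3: check by simulation.** Settings: 103 per arm, 78% versus 60%, 20,000 trials per setting, one continuous covariate, risk difference from a linear model with HC2 robust standard error. Type I error was checked at 60% versus 60%.

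| R² (covariate AUC) | Power, chi-square | Power, adjusted | Type I, chi-square | Type I, adjusted |
|---|---|---|---|---|
| 0 (0.50) | 80.3% | 79.9% | 5.4% | 5.2% |
| 0.049 (0.63) | 80.6% | 82.1% | 5.4% | 5.2% |
| 0.088 (0.68) | 81.1% | 84.0% | 5.3% | 4.8% |
| 0.134 (0.72) | 80.6% | 85.0% | 5.4% | 5.0% |

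A second simulation used logistic standardisation with three covariates: 50% of lesions previously treated, 30% cephalic arch, and one continuous variable. With assumed odds ratios for patency loss of 2 / 1.5 / 1.3 per SD, power rose from 80.5% to 82.2%. With 2.5 / 2 / 1.3 it reached 83.5%, and with 3 / 2 / 1.5 it reached 84.7%. Type I error was 5.0–5.7% adjusted and 5.2–5.6% unadjusted. With four covariates under the same assumed odds ratios, the gain was about 0.6 to 3.5 points. With no prognostic effect, about 0.8 points were lost.

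**Step 4: dependence on the assumed rates.** If control patency were 63.0%, a plain-angioplasty figure cited in section 1.7, power at 103 per arm would be 65.8% unadjusted, 68.0% at R² = 0.05 and 70.4% at R² = 0.10. At the 78.7% versus 47.9% of the stent-graft trial in the same section, unadjusted power is already 99.7%.

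**The case against.** The strongest reply is that nothing here is wrong. Under randomisation the unadjusted chi-square is valid, the trial was sized on that same test, and it reaches its target. Chance imbalance is already allowed for in the error rate and the interval. That stands: a reader might infer that the trial is underpowered or the estimate biased, and the documents support neither.

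A reader might also take the 2–4 points as established. They are not. No visible passage says that lesion length, RVD, arch location, earlier intervention or access age predicts 6-month TLPP, or how strongly. The nearest sentence, "Recurrent lesions after PTA have been demonstrated to have a higher proliferative index than the primary lesion", is in section 1.9 on central veins and concerns a proliferative index, not patency in AVF peripheral outflow veins. It should not be cited as evidence of a prognostic effect.

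Thirdly, a reader might call the gain free. It needs no subjects or visits, but section 9.0 is part of the protocol, and section 12.3 requires FDA and then IRB/EC approval of significant changes affecting scientific soundness or data validity. Section 9.8 rules out imputation in all analyses, so filling in a missing covariate needs an explicit exception. Physicians and subjects are unblinded (6.4.3), so a late change to the primary test would be open to challenge.

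On type I error, 5.7% is above nominal by more than simulation error: √(0.05·0.95/20,000) is about 0.15 points. The chi-square reached 5.6% in the same exercise, so adjustment is no materially worse, but it is not exact.

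Finally, section 9.4 and parts of the procedure and eligibility text are absent from the public document. An adjusted supportive analysis there cannot be excluded. The primary test itself is clear in 9.10.

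**Conclusion.** The point holds as a modest, optional improvement. The AVF primary test is sound and meets its stated 80% power, but it makes no use of variables already collected before randomisation. At 103 evaluable per arm, adjustment would raise power from 80.2% to about 82–84% if those variables explain 5–10% of outcome variance. Over a wider range, the change runs from a loss of under one point (no prognostic value) to a gain of about 8 points (R² = 0.20). The result rests on the plan's 78% and 60% and on an R² that the documents do not supply. If the control rate is well above 60%, adjustment helps by a few points but does not restore 80% power.

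**What to change.** In section 9.10, make the AVF primary test and 95% confidence interval the standardised (marginal) difference in 6-month TLPP proportions. Estimate it from a logistic model with treatment and a short fixed covariate list, using a robust or influence-function standard error, preferably with a small-sample correction. Suggested covariates:

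- lesion length and RVD, as recorded by the operator before randomisation;
- cephalic arch, yes or no, after confirming that target lesion location is recorded before randomisation in both arms;
- earlier intervention at the target site, only if derivable from the recorded intervention locations, since no visible field says whether the target lesion itself was treated before.

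Keep the list short, because weak covariates return nothing and cost a little. The superiority hypothesis in 9.7 and the evaluable set in 9.10 stay as they are, and the unadjusted chi-square becomes the supportive analysis.

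The cost is a protocol amendment and a little programming, with no new data. The amendment should name the covariates, the model, the variance estimator and the missing-covariate rule, the last as a stated exception to section 9.8. It must be fixed before any outcome data by arm are seen, and approved under section 12.3 if it counts as a significant change. If that point has passed, leave the chi-square as primary and report the adjusted difference as supportive only.
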